# Safety/tolerability (adverse events)

Adverse events are reported on the adverse event log.

# Acceptability of treatment (assessed 3 months after resolution of EP by Likert score).

Acceptability of treatment is reported on the acceptability and return of menses questionnaire.

# Return to menses (assessed 3 months after resolution of EP)

Return to menses is reported on the acceptability and return of menses questionnaire.

Women will be excluded from this analysis if resolution data unknown (resolution data unknown if a woman is not followed up to a hCG  $\leq$ 15 IU/L and we do not have confirmation from site if surgery was performed).

If a woman's menses have returned based on the following responses to 'when did your period return after your treatment', then they will considered as having an event and time to menses will be derived as follows:

Time to menses=10 days if 'when did your period return after your treatment'=1-2 weeks. Time to menses=24 days if 'when did your period return after your treatment'=3-4 weeks. Time to menses=38 days if 'when did your period return after your treatment'=5-6 weeks. Time to menses=52 days if 'when did your period return after your treatment'=7-8 weeks. Time to menses=66 days if 'when did your period return after your treatment'=9-10 weeks. Time to menses=80 days if 'when did your period return after your treatment'=11-12 weeks.

If 'when did your period return after your treatment'=Not returned then the woman will be regarded as not having an event and will be censored at the point of questionnaire completion. Time to form completion for censoring will be derived as follows:

Time to form completion (days) = (Date of questionnaire completion-Date of resolution\*)

\*Date of resolution is date of surgery (salpingectomy or salpingostomy/salpingostomy) or earliest date post-randomisation where hCG level is  $\leq$ 15 IU/L. If a date of resolution is missing (no surgery and not followed up to a hCG  $\leq$ 15 IU/L) and site have confirmed woman's pregnancy has resolved and no surgery performed, date of most recent hCG measurement will be used as date of resolution.

If no menses data is available, a woman will be censored at time zero (a continuity correction of 0.01 days will be applied to such instances, as Stata is unable to process zero time).

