#### **Trial methods**

#### Trial design

GEM3 is a multi-centre, prospective, double-blind, superiority, parallel group, phase III placebocontrolled randomised trial. Participants will be recruited in the United Kingdom (UK). Participants will be randomised to MTX and gefitinib or MTX and placebo. See trial schema in Appendix B.

Trial interventions

The intervention group will be given a single-dose intramuscular MTX (50 mg/m^2) injection (standard care) with seven daily doses of oral gefitinib (250 mg). The control group will be given a single-dose intramuscular MTX (50 mg/m^2) injection with seven daily doses of placebo (matched to the oral gefitinib tablet).

Primary outcome measure

The primary outcome is surgical intervention for the treatment of EP (salpingectomy or salpingostomy by laparoscopy or laparotomy).

Secondary outcome measures

Secondary outcomes are as follows:

Use of additional MTX (as directed by standardised expected change in serum hCG level).

Time to hCG resolution (days) from randomisation until hCG levels  $\leq$ 15IU/L.

Number of hospital visits associated with treatment until resolution or scheduled/emergency surgery.

Safety/tolerability (adverse events (AE)).

Acceptability of treatment (assessed 3 months after resolution of EP by Likert score).

Return to menses (assessed 3 months after resolution of EP).

Timing of outcome assessments

The schedule of trial procedures and outcome assessments are given in Appendix C.

Randomisation

Participants will be randomised in a 1:1 ratio to either MTX and gefitinib or MTX and placebo.

Randomisation will be provided by a secure online randomisation system at the Birmingham Clinical Trials Unit (BCTU) using a minimisation algorithm incorporating the following factors:

```
Baseline serum hCG levels (<1500 IU/L, \geq1500 to <2500 IU/L, \geq2500 IU/L)
Body Mass Index (BMI) (<25 kg/m^2, \geq25 kg/m^2)
Ectopic size on ultrasound (<2cm, \geq2cm)
Centre
```

A 'random element' will be included in the minimisation algorithm, so that each participant has a probability (unspecified here), of being randomised to the opposite intervention that they would have otherwise received. Full details of the algorithm used will be stored in a confidential document at BCTU.

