#### Sample size

The target sample size of 328 participants is based on data taken from the Phase II study (GEM2), published cohort data [1] and an audit of Edinburgh and Imperial of women undergoing usual care (2012; focusing on those participants with serum hCG >1000 IU/L). The cohort and audit data suggest a 30% rate of surgical intervention in the MTX group, with 15% expected in the MTX and gefitinib group (actual figure from the phase II study was 14% but this has been conservatively rounded up). To detect this absolute difference in proportions of 15% with 90% power and an alpha error rate of 5%, a total of 322 participants would need to be randomised (161 per group). Assuming and adjusting for a 2% loss to follow-up rate, 328 participants need to be recruited.

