Time to event data (return to menses) will be summarised using medians and interquartile ranges. A Cox Proportional Hazard model will be fitted to generate an adjusted hazard ratio (and 95% CI) and a Kaplan Meier plot will be produced to assess the data visually.

Binary outcomes (additional MTX, adverse events) will be analysed as per the primary outcome.

Categorical outcomes of an ordinal nature (acceptability of treatment measured using a Likert scale) will be summarised using frequencies and percentages. An ordinal logistic regression model will be used to generate adjusted odds ratios (and 95% CIs).

For secondary outcome measures which measure counts (number of hospital visits associated with treatment until resolution or scheduled/emergency surgery), this data will be summarised using medians with interquartile ranges. If appropriate, a Poisson model will be used to generate incidence rate ratios (and 95% CIs). An offset term will be included in each model to account for length of exposure time (see data manipulations (Appendix D) for how this will be derived). A negative binomial regression model may be considered if the data are overdispersed.

Analysis methods – exploratory outcomes and analyses

Any data that does not form a pre-specified outcome will be presented using simple summary statistics by intervention group (i.e. numbers and percentages for binary data and means (or medians) and standard deviations (or inter-quartile ranges) for continuous normal (or non-normal) data).

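### Return to menses counts events from treatment but censoring from resolution, and gives no code to a period that returns after week 12 but before the questionnaire

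*SAP*

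**What the plan says.** SAP section 4.4 lists the outcome as "Return to menses (assessed 3 months after resolution of EP". Section 9.6 says how it is analysed: "A Cox Proportional Hazard model will be fitted to generate an adjusted hazard ratio (and 95% CI) and a Kaplan Meier plot". Medians and interquartile ranges are also reported.

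Appendix D derives the variable as follows.

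- **Events.** A questionnaire item about return after treatment is answered in two-week bands, coded 10, 24, 38, 52, 66 and 80 days. The last is "Time to menses=80 days if 'when did your period return after your treatment'=11-12 weeks".
- **Censoring.** "If 'when did your period return after your treatment'=Not returned then the woman will be regarded as not having an event", and her time is "Time to form completion (days) = (Date of questionnaire completion-Date of resolution". Resolution is the date of surgery or of the first hCG at or below 15 IU/L. If both are lacking but the site confirms resolution without surgery, it is the date of the last hCG.
- **Missing data.** "If no menses data is available, a woman will be censored at time zero", implemented as 0.01 days.
- **Exclusion.** "Women will be excluded from this analysis if resolution data unknown".

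**The concern.** The event clock starts at treatment and the censoring clock at resolution. They differ by the whole interval from treatment to resolution, which is itself the subject of another secondary outcome and is cut short by surgery, the primary outcome.

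The coding also stops too early for its own schedule. A questionnaire three months after resolution reaches a woman more than 12 weeks after treatment, yet the longest codable return is 12 weeks. If her period came back in between, she is neither 'Not returned' nor in any band, and the only residual rule is the one for missing data. Applying that rule would remove the slowest returners from every risk set and make the Kaplan-Meier curve and median too early. The loss would be heavier in whichever arm resolves more slowly. The exclusion for unknown resolution also removes women whose event times, as coded, do not use that date.

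**Working it through.** **The plan's own figures.** The SAP states no figure for this outcome. Its sample size (30% v 15%, 90% power, two-sided 5%, pooled variance) reproduces at 161 per group, 322 in all. Inflating for 2% loss gives 322/0.98 = 328.6 against the stated 328. None of this bears on the point.

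**Step 1: does the censoring origin matter by itself?** Last event time: 80 days (Appendix D). Questionnaire: three months after resolution, about 13 × 7 = 91 days. If resolution falls R days after treatment, a 'Not returned' woman is censored at about 91 days on the resolution clock or 91 + R on the treatment clock. Both exceed 80, so she is in every risk set either way, and neither the Cox estimate nor the Kaplan-Meier curve to day 80 changes. The origin matters only for questionnaires completed before about day 80 after resolution. It misstates follow-up time in every case where R > 0.

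**Step 2: how wide is the uncoded window?** Codes end at 12 × 7 = 84 days after treatment and the questionnaire falls at about 91 + R. The window has length (91 + R) − 84 = 7 + R days.

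| R (days) | Questionnaire, days after treatment | Uncoded days | Length |
|---|---|---|---|
| 0 | 91 | 85-91 | 7 |
| 14 | 105 | 85-105 | 21 |
| 28 | 119 | 85-119 | 35 |
| 42 | 133 | 85-133 | 49 |

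The window depends on R, hence on speed of resolution and on surgery. The SAP's design assumption is that surgery differs by arm: "The cohort and audit data suggest a 30% rate of surgical intervention in the MTX group", against 15% with gefitinib.

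**Step 3: illustrative size.** The SAP gives no distribution of resolution or menses times, so every input here is an assumption:

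- 40,000 women in all, allocated to the two arms at random
- time to resolution lognormal (log SD 0.5), control median 14, 28 or 42 days, multiplied by 0.8 with gefitinib; surgery not modelled separately
- time from resolution to menses lognormal, median 32 days (log SD 0.45), the same in both arms, with 5% never returning
- questionnaire 91 to 105 days after resolution

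| Assumed control median | 14 d | 28 d | 42 d |
|---|---|---|---|
| Uncoded share of all returns | 4% | 16% | 34% |
| Uncoded, gefitinib v placebo | 3.6% v 5.1% | 12% v 19% | 27% v 40% |
| HR, treatment clock, full follow-up | 1.14 | 1.21 | 1.29 |
| HR, treatment clock, cut at day 84 | 1.15 | 1.29 | 1.43 |
| HR, resolution clock | 1.00 | 0.98 | 0.99 |
| SAP coding, late returns sent to time zero | 1.10 | 1.12 | 1.13 |
| SAP coding, late returns kept as not returned | 1.12 | 1.24 | 1.37 |

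Switching only the censoring origin left both SAP rows unchanged. With questionnaires moved to 70-84 days after resolution, it shifted the hazard ratio by at most about 0.03. The material difference is between the last two rows, and the SAP does not choose between them.

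**The case against.** **The headline mismatch is nearly harmless.** This is right for on-time questionnaires (Step 1). A reader might infer from the two origins that the risk sets are corrupted and that the hazard ratio, median and plot cannot be interpreted. The censoring formula does not support that.

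**The time-zero rule may not apply.** It covers women with no menses data, and a woman who reports a late return has some. If she is kept at risk as not returned, the SAP coding comes close to a treatment-clock hazard ratio cut at 12 weeks (1.12, 1.24, 1.37 against 1.15, 1.29, 1.43). The inference that the model estimates neither clock therefore holds only under one handling of late returns. What stands is that the SAP does not state the handling, and the result depends on it.

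**Treatment is undefined and the form is not shown.** Women may have answered from resolution, which would fit the timing of the form and the exclusion for unknown resolution. The clocks would then agree and the uncoded window would shrink to about a week. This is possible, but the SAP does not say it.

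**The size is assumed and within trial precision.** With 328 women and, say, 250 events, the 95% limits are the estimate times or divided by exp(1.96 × √(4/250)) = 1.28. At a 28-day median the time-zero handling is out by a factor of 1.21/1.12 = 1.08 against full treatment-clock follow-up and 1.29/1.12 = 1.15 against the 12-week cut. That is fair, but it does not justify leaving the rule open.

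**Conclusion.** The derivation is internally inconsistent and incomplete as written. It uses two time origins without conversion, and has no code for returns between week 12 after treatment and the questionnaire.

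The first defect misstates follow-up and affects the hazard ratio only when questionnaires are completed before about day 80 after resolution. The second is the main risk: late returners can be lost at a rate that depends on time to resolution and on surgery. About 4% to 34% of returns are uncoded across assumed control medians of 14 to 42 days. The imbalance between arms rests on the further assumption that gefitinib shortens resolution by a fifth. All of this takes treatment to mean the start of treatment.

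Severity is moderate. This is one secondary outcome, reported without a p-value, and the primary outcome and sample size are unaffected.

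**What to change.** In Appendix D:

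1. State what treatment means in the questionnaire item.
2. Use that date as the single origin for events and censoring: the initial MTX date, or randomisation if MTX was not given. Censoring time becomes questionnaire date minus that date.
3. Censor at day 84 every respondent still without a coded return by then. This includes anyone who reports a return after week 12, who should not go to time zero. Women who answered 'Not returned' before day 84 are censored at their questionnaire date.
4. Drop the exclusion for unknown resolution data, which this clock does not need.

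If the form's treatment in fact means resolution, say so and use the resolution date as origin for both, with the same 12-week cap. The resolution date is then still needed.

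The cost is a few lines of Appendix D and a small change to the derivation. The randomisation, MTX and questionnaire dates are already used there. The form should be checked to see how a return after week 12 could be recorded.

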## Other measures

## Adherence

Reported on baseline (initial data collection) form. If 'Date of MTX' is non-missing then assume initial MTX injection given. Number of tablets of trial medication taken is reported on the post-treatment visit form, surgery form and withdrawal form. The proportion of trial medication taken will be calculated as follows based on two scenarios:

If a woman has resolved\* <7 days post-randomisation then:

Proportion of trial medication taken=Number of tablets taken/(Date of resolution-date of randomisation)

If a woman has not resolved\* <7 days post-randomisation then:

Proportion of trial medication taken=Number of tablets taken/7

A woman is considered adherent if the initial MTX injection is given and the proportion of trial medication taken is  $\geq 0.75$ . Any women who do not receive an initial MTX injection or their allocated intervention as a result of a clinical change in condition (clinical change requiring immediate surgery post-randomisation) will be considered adherent.

\*Resolution occurs when a woman receives surgery (salpingectomy or salpingostomy/salpingostomy) or her hCG levels fall  $\leq$ 15 IU/L.

#### Ethnicity

White (British/Irish, Other North/West European, East European, South European, Other White) Asian (Indian, Pakistani, Bangladeshi, Other Asian) Black (African, Caribbean, Black Other) Mixed (White/Black Caribbean, White/African, White/Asian, Any other mixed background) Other (Other, Other Oriental) Chinese (Chinese)

#### Woman's age at randomisation (years)

Maternal age=(Date of randomisation-DOB)/365.25
